6.3.3 Tracking labels

The trial intervention packs also contain a tracking label, which must be attached to the patient, to ensure that the trauma center is a) made aware of the patient's enrollment; and b) able to identify which treatment was administered. The tracking label is also used to collect a small amount of prehospital data.

This mechanism avoids having to access a randomization mechanism in real-time and having to carry multiple packs. The disadvantage is that, should a crew encounter more than one suitable patient per shift, some patients may be missed. In addition, in a small study, there is a possibility that, purely by chance, eligible patients may be preferentially encountered by EMS units randomized to either the intervention, or the control treatment. This risk will be reduced with a larger sample size.

6.4 Consent (EFIC)

PhoXSTAT is an Exception from Informed Consent (EFIC) trial. We have extensive experience conducting major trauma trials under EFIC rules. Through our activities with the national Resuscitation Outcomes Consortium (ROC), we have executed eight trials on cardiac arrest or major trauma patients using EFIC. We are experienced with all aspects of EFIC, including communicating with the targeted communities, delivering information to patients and their families, and disseminating study information and results. Examples of studies that we have successfully carried out under EFIC include: ROC Hypertonic Saline Trial, ROC Hypotensive Resuscitation Trial, PROPPR, and the ROC TXA Trial. We have also conducted EFIC for numerous cardiac arrest trials.

All patients participating in the trial, regardless of whether allocated to receiving the intervention, or control treatment, are likely to benefit. Those receiving treatment with

XSTAT[®] will benefit from its probable hemostatic action. Patients randomized to control treatment will also benefit, because they will be part of a carefully designed study to assess the safety of treatment and will thus receive more clinical attention than patients who are not participating in the trial. The severity of junctional injuries is often underestimated by clinicians, with serious consequences, and this benefit is therefore tangible.

The procedures outlined below are based upon procedures that have been historically approved by the UAB Institutional Review Board and other related agencies such as the US Army Medical Research and Materiel Command (USAMRMC) Human Research Protection Office (HRPO). The nature and risk/benefit profile of XSTAT[®] is similar to these prior trials.

Because of the time-critical nature of hemorrhage care, the trial will be carried out under "Exception from informed consent required for emergency research" (EFIC) rules outlined in the guidance document "Waiver of Informed Consent Requirements in Certain Emergency Research" (Federal Register, Vol. 61, pp. 51531-51533, November 1, 1996 - http://www.gpo.gov/fdsys/pkg/FR-1996-10-02/html/96-24968.htm), OHRP "Basic HHS Policy for Protection of Human Research Subjects" (45 CFR 46.101(i) http://www.hhs.gov/ohrp/humansubjects/guidance/45cfr46.html#46.101), and FDA regulations 21 CFR 50.24.23-25.

6.4.1 Conditions present for conduct under 21 CFR 50.23

The use of EFIC is justified, as per FDA regulations 21 CFR 50.24.23-25, because the victims of major trauma are:

- a) In a life-threatening situation that necessitates urgent intervention: Femoral and axillary arterial injuries are associated with high mortality
- b) Available treatments are unproven or unsatisfactory: Available treatments include tourniquets, direct and indirect pressure, and hemostatic dressings. Section 3.1.2 contains details of why these treatments are unsatisfactory.
- c) Collection of valid scientific evidence is necessary to determine the safety and effectiveness of the intervention: Preclinical and clinical studies conducted to date confirm the safety of the XSTAT device.

- d) Obtaining informed consent is not feasible because the subjects are not able to give their informed consent as a result of their medical condition: The patients who will be included in this trial will be suffering from life-threatening hemorrhagic chock (class 3, 30-40% of blood volume lost; class 4, 40% of more of blood volume lost). Class 3 hemorrhagic shock is associated with "changes in mental status". In class 4 hemorrhagic shock, "mental status becomes increasingly altered" (https://www.ncbi.nlm.nih.gov/books/NBK470382/). Patients who meet the inclusion criteria for the trial are therefore unlikely to have capacity to provide informed consent to participate.
- e) The intervention must be administered before consent can be obtained from the subject's legally authorized representative: The therapeutic window for controlling hemorrhage, before the patient exsanguinates, is small. The time required to contact a LAR could determine whether a patient who could have lived, dies.
- f) There is no reasonable way to identify prospectively individuals likely to become eligible for participation: Patients do not usually expect to suffer penetrating junctional injuries.
- g) Participation in the research holds out the prospect of direct benefit to the subjects: Preclinical and early clinical data suggest that there is a real possible and direct benefit to patients treated with the XSTAT device.
- h) The clinical investigation could not practicably be carried out without the waiver: There is no alternative means of carrying out this type of research.

In conformance with EFIC rules, measures to protect the rights and welfare of subjects will include, at least:

- a) Community consultation
- b) Public disclosure
- c) Independent data monitoring
- d) Notification of LAR or family members of a subject's enrollment in the trial, with opportunity to discontinue trial participation.

Community consultation and public disclosure will be performed prior to study enrollment and at the completion of the study in the form of multimedia press releases organized by the study team. Examples of communication activities may include town hall meetings, press releases, website postings, random-digit-dialing surveys, and the use of social

media (Facebook and Instagram). These communications will describe plans for the study, including potential risks and benefits, equipoise and a summary of the results of the study upon completion. Information regarding the study will also be available on the UAB website.

6.4.2 Informed consent by patient

As described above, patients who meet the inclusion criteria for the trial, including the presence of class 3 or 4 shock (which is associated with mental status changes), are very unlikely to have the capacity to provide consent. Furthermore, a detailed discussion of the risks and benefits of participation could results in life-threatening delays to treatment. However, as per 21 CFR 50.24(a)(6), if patients are deemed to have capacity, informed consent will be sought and documented.

6.4.3 Informed consent by LAR

In the rare scenario where a LAR/family member is immediately available and the opportunity for consent is present, a short script (appendix 3) providing information regarding the study will be made available to the LAR/family member, affording the opportunity to withdraw consent for the patient's participation.

If an arterial injury is present, the therapeutic window for intervention is extremely short. Depending on the severity of the injury, exsanguination can occur within minutes. Importantly, this time is measured from the time of injury, rather than the time of arrival of emergency medical services. Once present, paramedics will be working to resuscitate (with intravenous fluid or blood transfusions, and sometimes also intubation) and transport the patient to a facilitate capable of definitive hemorrhage control, as quickly as possible. Contacting a family member of LAR who is not present at the scene is therefore unlikely to be feasible – both because contact details will not be available, and because of the time required. Nevertheless, should a situation arise where this is possible, efforts will be made to contact family members and ask whether he or she objects to the subject's participation in the research, as required by 21 CFR 50.24(a)(7)(v). This discussion will also be guided by the script in appendix 3.

6.4.4 Consent for ongoing participation

Once a subject is enrolled in the study, the research team will make frequent attempts as soon as feasible to contact a LAR/family member to obtain permission for continued participation and provide an opportunity to withdraw. A verbal withdrawal will be considered binding. Attempts to contact a LAR/family member will include direct contact, telephone contact and written contact or any other contact options as approved by local IRB policy.

6.4.5 Death before consent can be obtained

In the event the subject does not survive following the traumatic injury, his/her information will be included in the data analysis. Written notification may be sent to the deceased's family regarding participation in this study, per local IRB policy. Due to the severity of the injuries incurred, it is difficult to specify the timeframe involved with obtaining the consent, however multiple attempts will be made to obtain consent prior to completion of the study.

6.4.6 Opt-out

The ability and method of "opting out" of the study will be determined by the UAB Institutional Review Board, with updating by the other two sites (USC and VUMC). Because the population eligible for enrollment includes all citizens in the study regions, it will not be possible to target specific individuals, although the UAB IRB may suggest specific age groups and ethnic groups, determined by trauma registry data. Citizens wishing to opt-out of the trial will be provided with an "opt-out" bracelet. EMS personnel will be trained to check for opt-out identifiers prior to enrolling any patient.

6.4.7 "Prospect of direct benefit"

Information from animal and preclinical studies, and early clinical use support the potential for the investigational product to provide a direct benefit to the individual subjects. Participation in this pilot trial holds out the prospect of direct benefit to the subjects because

a) The subjects are in a life-threatening situation that necessitates intervention. Specifically, the condition in question (junctional hemorrhage) is not well-

addressed with currently available treatments, and hemorrhage is frequently not controlled until the patient reaches hospital.

- b) Information from appropriate animal and other preclinical studies support the potential for the intervention to provide a direct benefit to the individual subjects.
- c) The risks associated with the investigation are reasonable in relation to what is known about the medical condition of the potential class of subjects, the risks and benefits of standard therapy, if any, and what is known about the risks and benefits of the proposed intervention or activity.

6.4.8 Choice of endpoints

This protocol is for a pilot trial. The FDA recognizes that it is important to obtain preliminary information on the effect of new treatments on a variety of outcomes, including biomarkers (e.g., measurement of brain infarcted area, degree and extent of acidosis) before proceeding to a study that evaluates effectiveness. This pilot trial will evaluate several possible endpoints which could be used in a future effectiveness trial, including a biomarker (lactate).

7. OUTCOMES

PhoXSTAT is a pilot trial, and consequently there is no "primary" outcome. As per the aims and objectives, the following will be evaluated:

7.1 Trial feasibility (Objectives 1-2)

We will evaluate the feasibility of a full efficacy/effectiveness trial, using the following parameters:

- a) Number of patients with penetrating junctional (femoral and axillary) zone injuries who are entered into the pilot trial, and randomized. (Objective 1)
- b) Ability to obtain baseline estimates of possible future primary and secondary outcomes for a full randomized clinical trial. (Objective 2)

7.2 XSTAT usability (Objectives 3 and 4)

In order to conduct a full trial, the device has to be usable. Usability will be evaluated in the prehospital and operating room setting.

7.2.1 Prehospital setting (Objective 3)

Many civilian penetrating injuries are caused by low energy transfer firearms (typically handguns). The resulting wounds can be small, which may make insertion of the XSTAT[®] device difficult. We will evaluate the usability of the device in the prehospital setting, by investigating the following:

- a) Ease of insertion
- b) Ease of deployment
- c) Overall satisfaction with the device

7.2.2 Operating room (Objective 4)

Use of the XSTAT device commits the patient and medical team to operative exploration of the wound, and retrieval of the sponges. We will evaluate surgeons' views on the device, by collecting data on the following:

- a) The ease of sponge removal
- b) The time required to remove the sponges

- c) The use of x-rays/image intensifiers to ensure complete removal of the sponges
- d) Overall satisfaction with the device

7.3 XSTAT safety (Objective 5)

Although XSTAT[®] is thought to be a low-risk device, we will nevertheless obtain formal data on its safety profile, which will include the following:

- a) Number of patients suffering allergic reactions or anaphylaxis
- b) Number of patients developing wound infections
- c) Number of patients developing tissue damage thought to be related to the insertion of the device or deployment of the sponges
- d) Number of patients suffering embolization of the sponges
- e) Number of patients who suffer inadvertent retention of sponges (beyond first operation)
- f) Number of patients in whom no vascular injury is identified

8. DATA COLLECTION

8.1 Personnel

All three participating PhoXSTAT sites have research assistants available in the emergency department. Research assistants initiate, and complete, the data collection for the trial.

8.2 Case Report Form

Data is initially collected using paper Case Report Forms (CRFs, appendix 2), and then transcribed into an electronic database. The electronic CRF uses the Research Electronic Data Capture (REDCap) system, a secure research database developed by NIH. Data logic checks are used to minimize data entry errors. Data audits are performed on a randomly selected 20% of enrolled subjects. When data are complete, and all suspect entries addressed, the database will be "locked" and exported to STATA or SAS for analysis.

8.3 Patients entered into pilot trial: Prehospital data collection

The PhoXSTAT trial requires the collection of a minimal amount of prehospital data – primarily relating to the usability and safety of the device. Each trial intervention pack contains a tracking label, which must be attached to the patient, using the cable tie supplied. The tracking label contains a mini-questionnaire. If the patient was allocated to treatment with Xstat, the following details must be completed:

8.3.1 Usability

Ease of insertion of device into wound

- a) Unable to insert (wound too small to accept device)
- b) Reasonably easy to use (wound accepted device with some manipulation)
- c) Easily inserted (wound accepted device without difficulty)

Ease of deployment of sponges

- a) Unable to deploy sponges
- b) Reasonably easy to deploy sponges (several sponges successfully injected)
- c) Easily deployed (majority or all of sponges successfully injected)

Overall satisfaction with the device

- a) Dissatisfied
- b) Neither satisfied nor dissatisfied
- c) Satisfied

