4.2.2 Device usability

- Objective 3: To evaluate the usability of the XSTAT[®] device, in the prehospital setting, in patients with junctional injuries, in terms of the insertion of the device, and deployment of the sponges. (RQ 4: "Is the XSTAT[®] device easy to use, in the prehospital setting?")
- Objective 4: To evaluate the usability of the XSTAT[®] device, in the operating room setting, in patients with junctional injuries, in terms of the removal of the sponges. (RQ 5: "Are the XSTAT[®] sponges easy to remove, in the operating room?")

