8.4.1 Physiological parameters

The following measurements are collected on admission:

- a) Systolic, diastolic, and mean blood pressure
- b) Heart rate
- c) Shock index
- 8.4.2 Usability

The ease of sponge removal

- a) Unable to remove all sponges
- b) Reasonably easy to remove all sponges
- c) Sponges easily removed

The time required to remove the sponges

- a) 1 hour or longer
- b) Between 5 and 59 minutes
- c) Less than 5 minutes

The use of x-rays/image intensifiers to ensure complete removal of the sponges

- a) Imaging not used due to patient's clinical condition
- b) Imaging not used as not available
- c) Imaging deemed unnecessary
- d) Imaging used

Outcome of imaging:

- a) Additional sponges seen on imaging
- b) No additional sponges seen on imaging

Overall satisfaction with the device

- a) Dissatisfied
- b) Neither satisfied nor dissatisfied
- c) Satisfied

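### The insertion and removal items have no level for a hard but achieved use, and the deployment item grades sponge count rather than effort, which weakens the answer to Objective 3 most

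*Protocol*

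**What the plan says.** Protocol section 4.2.2 asks under Objective 3 whether the device is easy to use before hospital, and under Objective 4 whether the "sponges easy to remove, in the operating room". Section 7.2 makes usability a condition for a full trial. Section 7.2.1 expects that small handgun wounds may make insertion difficult.

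Three ease items serve these questions, each with three levels.

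- Insertion (8.3.1): "Unable to insert (wound too small to accept device"; "Reasonably easy to use (wound accepted device with some manipulation"; "Easily inserted (wound accepted device without difficulty".
- Deployment (8.3.1): "Unable to deploy sponges"; "Reasonably easy to deploy sponges (several sponges successfully injected"; and a top level for the majority or all of the sponges injected.
- Removal (8.4.2): not all sponges could be removed; "Reasonably easy to remove all sponges"; and sponges easily removed.

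The tracking label (Appendix 1) repeats the insertion and deployment levels without the explanatory text in brackets. Forms 5 and 7 of the codebook (Appendix 2) also use three levels and print no anchors. Form 5 even labels the middle deployment level for wound 1 as ease of use rather than of deployment.

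Section 10.2 limits the usability analysis to XSTAT subjects and promises details for both categories. It sets no usability threshold and does not say how levels would be combined.

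**The concern.** On insertion and removal, nothing lies between failure and a level called reasonably easy. A crew that struggles before the device enters, and a surgeon who retrieves every sponge only with great effort, must choose an answer that says easy. The middle level then mixes slight manipulation with real difficulty, which is the distinction that section 7.2.1 gives as its reason for studying insertion.

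The deployment item has a different fault. Its name says ease, but its anchors in 8.3.1 say quantity.

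At stake is how well the pilot can answer the usability questions behind two of its five objectives. These are fixed response options. A statistical analysis plan can decide how levels are tabulated, but it cannot restore a category that was never collected.

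**Working it through.** The plan states no figure to reproduce. The check sets the response options side by side and follows where a hard but achieved use would be recorded.

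**Step 1. Where such a use lands under the section 8 wording**

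| Item | Case | Level recorded |
|---|---|---|
| Insertion | Achieved with difficulty | Middle: not a failure, and the top level requires no difficulty |
| Removal | All sponges out, with difficulty | Middle or top: the lowest level requires that sponges stayed behind |
| Deployment | Laborious, most sponges in | Top, because only the count is anchored |
| Deployment | Laborious, several sponges in | Middle |
| Deployment | Effortless, several sponges fill a small void | Middle |

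The last two rows share a level although the effort was opposite. The first deployment row takes the best level although the effort was great.

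**Step 2. What can be recovered for insertion**

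Let u, h, r and e be the true shares of uses that were impossible, hard but achieved, reasonably easy and easy, with u + h + r + e = 1. The form records:

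- lowest level: a = u
- middle level: b = h + r
- top level: c = e

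Hence h = b − r. Since r is not observed, all that is known is 0 ≤ h ≤ b. The same holds for removal if surgeons put hard but complete removals in the middle level, and if incompleteness is set aside.

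**Step 3. Whether other items supply the missing information**

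- *Objective 3.* Sections 7.2.1 and 8.3.1 list overall satisfaction, with a negative option. It is not on the sample label. It is also not in Form 5, whose fields 1 to 24 run without a gap and include the section that transcribes the label. The label and Form 5 record the number of devices and a single time of use, so neither gives a duration or a measure of effort.
- *Objective 4.* Section 8.4.2 and Form 7 (fields 96 to 99 and 112 to 115) record removal time, imaging, imaging result and surgeon satisfaction. A long removal is therefore visible, but the time bands disagree. Section 8.4.2 has less than 5 minutes, 5 to 59 minutes and "1 hour or longer". Form 7 has less than 5, 5 to 30, and 31 minutes or longer. A removal of 31 to 59 minutes is in the middle band of one and the longest band of the other.

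**Step 4. Removal: ease and completeness in one item**

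One unretrieved sponge after an effortless removal takes the lowest level, and a hard but complete removal takes a better one. The first pulls against the device and the second in its favor. Retention beyond the first operation is already a separate safety outcome (7.3 and 8.4.7).

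**The case against.** The strongest reply is that nothing is hidden if the levels are reported one by one. The protocol nowhere defines success as the two favorable levels together. Under the 8.3.1 anchors the top insertion level excludes difficulty, so its share is not inflated, and the middle level shows that some manipulation was needed. This stands. A reader might infer that the form will overstate ease by a known amount. If the two favorable levels were added, the sum would be b + c = 1 − u whatever the value of h, and would exceed r + e by exactly h. But the protocol states neither that pooling rule nor any value of h, so the documents support no such figure. What remains is that the middle level mixes mild and marked difficulty, and that crews do not see the anchors on the label.

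Three other strong readings also fail.

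- A reader might say that every hard but achieved use is forced into the middle level. For deployment that is not so: with most sponges delivered it takes the top level.
- A reader might take a low sponge count as a sign of difficulty. Section 5.2 asks only for enough sponges to fill the void and expects that some may not be deployed, so a low count may simply mean a small cavity.
- A reader might say that the pilot cannot detect difficulty at all. For Objective 4 that is too strong, given removal time, imaging and surgeon satisfaction.

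It is also fair that prehospital data are kept minimal on purpose (8.3) and that crews are treating patients in severe shock. That argues for a short remedy, not for leaving the scale as it is.

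**Conclusion.** The point holds as a weakness of the instrument. The insertion and removal items pool hard but achieved use with mild manipulation under wording that says easy, and the deployment item measures quantity under the name of ease. The loss is one of identification: for insertion, the share of hard but achieved uses is known only to lie between zero and the middle-level share. The protocol gives no basis for a narrower figure.

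Objective 3 is affected most and Objective 4 less. The analysis is descriptive and has no threshold, so no test or formal decision is biased. This is a cheap improvement rather than a flaw that undermines the trial.

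Two assumptions matter. The sample label is taken as complete. The codebook copy reviewed jumps from field 52 to field 84, so the statement on prehospital satisfaction covers the label and Form 5 only.

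**What to change.** Before enrollment:

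1. Give the insertion, deployment and removal items four ordered levels: unable; difficult but achieved; reasonably easy; easy.
2. Anchor the deployment levels to effort, not to the number of sponges injected.
3. Record completeness of removal (all sponges out: yes or no) separately from ease of removal.
4. Print the same options and anchors in 8.3.1, 8.4.2, the tracking label and Forms 5 and 7. While doing so, reconcile the removal-time bands in 8.4.2 and Form 7, and the satisfaction item in 8.3.1 with the label and Form 5.
5. State in 10.2 that each level is reported separately.

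The cost is one tick-box per item, a yes/no field on Form 7, and a slightly longer label for the crew. Treatment, randomization and sample size do not change. The change has to come before enrollment because the distinction cannot be reconstructed afterward.
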